10.3.3. Definition of Cardiovascular events

Not Applicable.

10.3.4. Definition of TEAE

TEAE Definition:

 • A TEAE is an event that emerges during treatment, having been absent pre-treatment or worsens relative to the pre-treatment state.

10.3.5. Recording, assessment and follow-up of AE, SAE, and pregnancies

10.3.5.1. AE and SAE recording

- When an AE/SAE occurs, it is the responsibility of the investigator to review all documentation (e.g., hospital progress notes, laboratory reports, and diagnostics reports) related to the event.
- The investigator will then record all relevant AE/SAE information.
- It is not acceptable for the investigator to send photocopies of the participant's medical records to GSK in lieu of completion of the required form.
- There may be instances when copies of medical records for certain cases are requested by GSK. In this case, all participant identifiers, with the exception of the

participant number, will be redacted on the copies of the medical records before submission to GSK.

- The investigator will attempt to establish a diagnosis of the event based on signs, symptoms, and/or other clinical information. Whenever possible, the diagnosis (not the individual signs/symptoms) will be documented as the AE/SAE.

10.3.5.2. Assessment of intensity

The investigator will make an assessment of intensity for each AE, SAE and device deficiency reported during the study and assign it to one of the following categories:

- **Mild:**
A type of AE that is usually transient and may require only minimal treatment or therapeutic intervention. The event does not generally interfere with usual activities of daily living.
- **Moderate:**
A type of AE that is usually alleviated with additional specific therapeutic intervention. The event interferes with usual activities of daily living, causing discomfort but poses no significant or permanent risk of harm to the research participant.
- **Severe:**
A type of AE that interrupts usual activities of daily living, or significantly affects clinical status, or may require intensive therapeutic intervention.

10.3.5.3. Assessment of causality

- The investigator is obligated to assess the relationship between the study interventions as described in [Table 4](#) and each occurrence of each AE/SAE/device deficiency. The investigator will use clinical judgment to determine the relationship.
- A reasonable possibility of a relationship conveys that there are facts, evidence, and/or arguments to suggest a causal relationship, rather than a relationship cannot be ruled out.
- Alternative causes, such as underlying disease(s), concomitant therapy, and other risk factors, as well as the temporal relationship of the event to study intervention administration, will be considered and investigated.
- For causality assessment, the investigator will also consult the product information for marketed products.
- The investigator must review and provide an assessment of causality for each AE/SAE and document this in the medical notes. There may be situations in which an SAE has occurred and the investigator has minimal information to include in the initial report to GSK. However, it is very important that the investigator always make an assessment of causality for every event before the initial transmission of the SAE data to GSK.

- Where multiple interventions are administered in the same visit, the investigator should specify, when possible, if the AE/SAE could be causally related to a specific study intervention. When a causal relationship to a specific study intervention cannot be determined, the investigator should indicate the AE/SAE to be related to all interventions
- The investigator may change their opinion of causality in light of follow-up information and send an SAE follow-up report with the updated causality assessment.

The causality assessment is one of the criteria used when determining regulatory reporting requirements.

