- Administration of nebulized 99mTc inhalation given 30 \pm 10 min after the last propellant intake. Measurement of retained radioactivity will be performed immediately after nebulized 99mTc administration (scintigraphic time="0") and then at 15, 30, 45, 60, 90, 120, 150, 180, 210, 240 min after nebulized 99mTc administration.
- All AEs will be collected from the start of study intervention until final discharge from the study (including washout period). All SAEs will be collected from the signing of the Informed consent form (ICF) until final discharge from the study (including washout period).

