6.1. Study Intervention Administered

Study intervention is presented in [Table 4](#).

Table 4 Study Intervention Administered

Intervention Label	Test Treatment	Reference Treatment	MCC gamma scintigraphy assessment
Intervention Name	Test propellant: HFA-152a, aka 1 – Difluoroethane	Reference propellant (HFA-134a, aka 1,1,1,2 – Tetrafluoroethane	Nebulized radiolabelled saline solution
Intervention Description	repeated doses: 6 days, 4 inhalations twice daily (BID)+last administration on the morning of Day 7	repeated doses: 6 days, 4 inhalations twice daily (BID)+last administration on the morning of Day 7	Saline solution containing radiolabeled ^{99m} Tc colloidal sulphur
Route of administration	Oral inhalation	Oral inhalation	Oral inhalation
Use	Propellant for Ventolin	Propellant for Ventolin	Enable assessment of MCC via scintigraphy imaging
Source	GSK	GSK	Clinical site CCI
Packaging and Labeling	Study intervention will be provided in a canister fitted with a metering valve within an actuator. Each canister will be labeled as required per country requirement.	Study intervention will be provided in a canister fitted with a metering valve within an actuator. Each canister will be labeled as required per country requirement.	Labelled as per the country requirements

The study intervention will be administered with the participant in the upright, seated position. Dosing for each individual participant will be at around the same time in the morning and in the evening (time interval 12±3 hour) BID on each dosing day.

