Relationship to study treatment, as indicated by the investigator, is classified as “not related” or “related”. AEs with a missing relationship to study treatment will be recorded as “related” to study treatment. If a participant reports the same AE more than once within an SOC/PTs, the AE with the worst-case relationship to study treatment will be used in the corresponding relationship summaries.

The following summaries (counts and percentages) will be presented for drug-related AEs and SAEs for on-treatment period

- Summary of drug-related (Propellant) AEs by overall frequency (SOC and PT), by test /reference propellant.
- Summary of drug-related (Propellant) SAEs by overall frequency (SOC and PT), by test /reference propellant.
- Summary of serious fatal and non-fatal drug-related adverse events (Propellant) will be created by overall frequency (SOC and PT), by test /reference propellant.

- Summary of drug-related (Propellant) non-serious AEs by SOC and PT will also be presented , by test /reference propellant.
- Summary of drug-related (99mTc-sulphur colloid inhalation) AEs by overall frequency (SOC and PT)
- Summary of drug-related (99mTc-sulphur colloid inhalation) SAEs by overall frequency (SOC and PT)

AEs and SAEs by severity:

Adverse event severity is categorised as mild, moderate, severe. Adverse events starting after the first dose of study treatment with a missing severity will be classified as severe. If a participant reports an AE more than once within an SOC/PTs, the AE with the worst-case (maximum) severity will be used in the corresponding severity summaries.

The following summaries (counts and percentages) will be produced for severity of AEs and SAEs by SOC, PTs, and maximum severity in overall (on- and post-treatment) and on-treatment period.

- Summary of AEs by SOC and PT and maximum severity
- Summary of SAEs by SOC and PT and maximum severity

AEs and SAEs leading to permanent discontinuation of study treatment

The below summaries (counts and percentages) for AEs and SAEs leading to permanent discontinuation of study treatment by SOC and PTs and maximum severity will be generated in overall (on- and post-treatment) and on-treatment period.

- Summary of AEs leading to permanent discontinuation of study treatment by SOC and PT
- Summary of SAEs leading to permanent discontinuation of study treatment by SOC and PT

Adverse events analyses including the analysis of AEs and SAEs will be based on GSK Core Data Standards(IDSL).

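### Day 7 adverse events that cannot be assigned to propellant or colloid enter both sets of drug-related tables and pull the propellant-related Test/Reference comparison toward no difference (minor)

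*Protocol*

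**What the plan says.** Protocol 10.3.5.3 requires causality to be assessed against the study interventions of Table 4. That table lists Test, Reference and, in a third column, the nebulized 99mTc colloid (use: "Enable assessment of MCC via scintigraphy imaging"), so the colloid is covered. Where several interventions are given at one visit, "the investigator should specify, when possible, if the AE/SAE could be causally related to a specific study intervention". The fallback follows: "When a causal relationship to a specific study intervention cannot be determined, the investigator should indicate the AE/SAE to be related to all interventions". The same list says that a reasonable possibility of a relationship means there are "facts, evidence, and/or arguments to suggest a causal relationship, rather than a relationship cannot be ruled out".

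The Schedule of Activities places the colloid 30 ± 10 minutes after the last propellant dose, on Day 7 of each period. Protocol Table 2 names local respiratory irritation as a risk for the propellants, and local tolerability problems and bronchospasm as risks for the colloid. It gives no rates.

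SAP 4.5.2 plans, for the on-treatment period, a "Summary of drug-related (Propellant) AEs by overall frequency (SOC and PT), by test /reference propellant", with companion tables for serious and non-serious events. It plans separate tables for events related to the colloid. Its treatment-emergent definition runs to one day after treatment stops, so events in the hours after nebulization are included.

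**The concern.** The SAP keeps two sets of drug-related tables, which should let a reader tell propellant tolerability from colloid tolerability. An event coded to both interventions appears in both sets, and no summary described in the SAP marks it. Because the same colloid is given in both periods, such events can be added on the Test side and the Reference side alike.

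Protocol Table 2 names as a risk that Test may have a different local tolerability profile from Reference. Over-attribution is cautious when an absolute rate is read. In a comparison it works the other way, because it makes the two propellants look more alike. The all-cause tables do not supply the missing contrast, since they contain colloid events in both periods too.

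**Working it through.** The documents state no AE rate, safety margin or safety power, so there is no figure to reproduce. The check has three steps.

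**1. The path of one event.** A participant has an airway symptom after nebulization on Day 7, and the investigator cannot tell which inhalation caused it. Under Protocol 10.3.5.3 it is recorded as related to all interventions. Under SAP 4.5.2 it is attributed to the period in which it occurs, hence to one propellant. It enters that propellant's column and also the colloid table. If the same participant had the same preferred term earlier in the period, judged unrelated, the SAP's worst-case relationship rule still counts that participant as propellant-related.

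**2. The effect on the comparison.** Let p_T and p_R be the true proportions with a propellant-caused AE on Test and Reference. Let q be the proportion with a colloid-caused AE coded to all interventions, so q = (rate of colloid-caused AEs) × (share that cannot be attributed). Assume q is the same in both periods and independent of propellant-caused events. Then:

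- observed proportion = 1 − (1 − p)(1 − q)
- observed difference = (1 − q)(p_T − p_R)

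With assumed p_T = 15%, p_R = 5% and the 24 planned participants on each treatment:

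| q | Test | Reference | Difference (points) | Ratio | Participants of 24 |
|---|---|---|---|---|---|
| 0% | 15.0% | 5.0% | 10.0 | 3.00 | 3.6 v 1.2 |
| 5% | 19.25% | 9.75% | 9.5 | 1.97 | 4.6 v 2.3 |
| 10% | 23.5% | 14.5% | 9.0 | 1.62 | 5.6 v 3.5 |
| 20% | 32.0% | 24.0% | 8.0 | 1.33 | 7.7 v 5.8 |
| 30% | 40.5% | 33.5% | 7.0 | 1.21 | 9.7 v 8.0 |

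For example, at q = 20%: 1 − 0.85 × 0.80 = 0.320 and 1 − 0.95 × 0.80 = 0.240. With a smaller assumed contrast of 10% v 5%, the ratio of 2.0 becomes 1.49, 1.31 and 1.17 at q = 5%, 10% and 20%, and the difference of 5 points becomes 4.75, 4.5 and 4.0.

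The effect is marked on the ratio scale and small on the difference scale. At q = 20% the expected excess on Test falls from 24 × 0.10 = 2.4 participants to 24 × 0.08 = 1.9. The SAP plans counts and percentages, not ratios.

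**3. What could be seen without the colloid.** Each period has 6 × 2 + 1 = 13 propellant doses. Twelve are given on Days 1 to 6, and the 13th precedes nebulization by 20 to 40 minutes. AEs with onset before nebulization therefore give a Test/Reference contrast free of that period's colloid without any causality judgement. SAP 4.5.2 has a rule for an AE whose time is missing on a dosing day, which implies that onset times are collected. Protocol 8.7.1 uses the start of nebulization as the start of the cough record.

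**The case against.** A reader might infer that all irritation after the colloid will be counted as propellant-related. The documents do not support that. The rule is a fallback after attribution where possible, and the investigator must weigh timing. A participant who tolerated 12 supervised doses and coughs only once nebulization begins gives evidence pointing to the colloid. Nothing in the documents shows that attribution will usually fail.

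A reader might also infer that the secondary safety endpoint is biased by the rule. It is not: that endpoint is the incidence of all AEs and SAEs whatever the cause, and SAP 4.5 excludes formal comparison of safety data. No test, margin or power is lost.

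Nor is Protocol 10.3.5.3 necessarily self-contradictory. Its evidence threshold can be read as deciding whether an event is related at all, and the fallback as allocating a related event among interventions given together. The wording could be clearer, but the two statements can stand side by side.

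The assumed rates may also be high. The protocol reports no local respiratory irritation in the pilot PK study, calls bronchospasm from inhaled particulates rare, and describes inhaled colloid as safely used since the 1980s. The listings of all AEs by treatment and period would allow some reconstruction by hand, and the output specifications, which are not in the documents, may hold more detail.

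These objections limit the point to supportive tables and make its size uncertain. They do not change the fact that an event coded to both interventions enters both table sets, or that no summary described in the SAP gives a contrast before the colloid.

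**Conclusion.** The point holds in a limited form and is minor. Day 7 events that cannot be attributed to propellant or colloid enter both the propellant-related and the colloid-related tables, and any such events pull the descriptive propellant-related comparison toward no difference. The size cannot be known from the documents. With q equal in both periods and independent of propellant events, the difference shrinks by 1 − q, and with q = 0 nothing changes. If airways irritated by one propellant reacted more to the colloid, q would differ between treatments and the factor would not apply. The all-cause endpoint is not altered by the coding rule, although it also includes colloid events in both periods.

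**What to change.** Leave the causality rule and SAE reporting as they are, since causality feeds regulatory reporting. In SAP 4.5.2:

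- Split the all-cause and the propellant-related AE summaries, by Test and Reference, into onset before versus at or after the start of that period's Day 7 99mTc nebulization.
- Show events coded to both propellant and colloid in a separate row, still counted as related.
- Describe the first part as the contrast free of that period's colloid, covering the 12 doses of Days 1 to 6 and the short interval after the 13th. It is not the complete propellant comparison.
- Place a Day 7 AE with no onset time in the 'at or after' part.

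The cost is extra programming of existing summaries and smaller cells. Late propellant effects, and most effects of the 13th dose, fall in the 'at or after' part. Two limits should be stated: the Day 7 saline training inhalation also falls before nebulization, and in Period 2 the first part follows the Period 1 colloid, though after the washout.

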10.3.5.4. Assessment of outcomes

The investigator will assess the outcome of all serious and nonserious unsolicited AEs recorded during the study as:

- Recovered/resolved
- Recovering/resolving
- Not recovered/not resolved
- Recovered with sequelae/resolved with sequelae
- Fatal (SAEs only).

10.3.5.5. Follow-up of AEs, SAEs, pregnancies or any other events of interest

- The investigator is obligated to perform or arrange for the conduct of supplemental measurements and/or evaluations as medically indicated or as requested by GSK to elucidate the nature and/or causality of the AE or SAE as fully as possible. This may include additional laboratory tests or investigations, histopathological examinations, or consultation with other health care professionals.
- If a participant dies during participation in the study or during a recognized follow-up period, the investigator will provide GSK with a copy of any postmortem findings including histopathology if available.
- New or updated information will be recorded in the originally submitted documents.
- The investigator will submit any updated SAE data to GSK within 24 hours of receipt of the information.

After the initial AE/SAE/pregnancy or any other event of interest, the investigator is required to proactively follow each participant at subsequent visits/contacts. All SAEs, will be followed until the event is resolved, stabilized, otherwise explained, or the participant is lost to follow-up.

Other nonserious AEs must be followed until follow-up visit or until the participant is lost to follow-up.

Follow-up during the study

AEs documented at a previous visit/contact and defined as not recovered/not resolved or recovering/resolving will be reviewed at subsequent visits/contacts until follow-up visit or until the participant is lost to follow-up.

If a participant dies during their participation in the study or during a recognized follow-up period, GSK will be provided with any available postmortem findings, including histopathology, if available.

Follow-up of pregnancies

Pregnant partners of male participants will be followed to determine the outcome of the pregnancy. At the end of the pregnancy, whether full-term or premature, information on the status of the mother and child will be forwarded to GSK using the paper pregnancy follow-up report and the AE Report if applicable. Generally, the follow-up period does not need to be longer than 6 to 8 weeks after the estimated date of delivery.

Regardless of the reporting period for SAEs in this study, if the pregnancy outcome is an SAE, it should always be reported as such.

Furthermore, the investigator must report any SAE occurring as a result of a poststudy pregnancy that is considered by the investigator to be reasonably related to the study intervention, to GSK as described in the Section [10.3.5.7](#).

10.3.5.6. Updating of SAE and pregnancy information after removal of write access to the participant's eCRF

When additional SAE or pregnancy information is received after write access to the participant's eCRF is removed, new or updated information should be recorded on the appropriate paper report, with all changes signed and dated by the investigator. The updated report should be sent to the Study contact for reporting SAEs (refer to Section [8.4.1](#)).

10.3.5.7. Reporting of SAEs and pregnancies

SAE Reporting to GSK via an Electronic Data Collection Tool

- The primary mechanism for reporting an SAE to GSK will be the electronic data collection tool.
- If the electronic system is unavailable, then the site will use the paper SAE data collection tool (see next section) to report the event within 24 hours.
- The site will enter the SAE data into the electronic system as soon as it becomes available.
- After the study is completed at a given site, the electronic data collection tool will be taken offline to prevent the entry of new data or changes to existing data.

- If a site receives a report of a new SAE from a study participant or receives updated data on a previously reported SAE after the electronic data collection tool has been taken offline, then the site can report this information on a paper SAE form (see next section) or to the medical monitor by telephone.
- If the site during the course of the study or poststudy becomes aware of any serious, nonserious AEs, pregnancy exposure, related to any GSK non-IMP they will report these events to GSK or to the concerned competent authority (CA) via the national spontaneous reporting system. These will be classified as spontaneous ICSRs.
- Contacts for SAE reporting can be found in Section 8.4.9.

SAE Reporting to GSK via Paper Data Collection Tool

- Email/facsimile transmission of the SAE paper data collection tool is the preferred method to transmit this information to the medical monitor.
- In rare circumstances and in the absence of email/facsimile equipment, notification by telephone is acceptable with a copy of the SAE data collection tool sent by overnight mail or courier service.
- Initial notification via telephone does not replace the need for the investigator to complete and sign the SAE data collection tool within the designated reporting timeframes.
- Contacts for SAE reporting can be found in Section 8.4.9.

10.4. Appendix 4: Contraceptive and barrier guidance

10.4.1. Definitions

10.4.1.1. Woman of Childbearing Potential (WOCBP)

Women in the following categories are considered WOCBP (fertile):

- Adolescents of childbearing potential: Tanner stage ≥ 2 (post-thelarche) irrespective of the occurrence of menarche or following menarche.
- From the time of menarche until becoming postmenopausal unless permanently sterile (see below)

Note: Menarche is the first onset of menses in a young female. Menarche is normally preceded by several changes associated with puberty including breast development and pubic hair growth.

10.4.1.2. Woman of Nonchildbearing Potential (WONCBP)

Women in the following categories are considered WONCBP:

- Permanently sterile due to one of the following procedures:
 - a. Documented hysterectomy

- b. Documented bilateral salpingectomy
- c. Documented bilateral oophorectomy

For permanently sterile individuals due to an alternate medical cause other than the above, (e.g., Mullerian agenesis, androgen insensitivity, gonadal dysgenesis), investigator discretion should be applied to determining study entry. If reproductive status is questionable, additional evaluation should be considered.

Note: Documentation can come from the site personnel's review of the participant's medical records, medical examination, or medical history interview.

- **Postmenopausal female**

A postmenopausal state is defined as no menses for 12 months without an alternative medical cause.

- A high FSH level in the postmenopausal range may be used to confirm a postmenopausal state in women not using hormonal contraception or (HRT). However, in the absence of 12 months of amenorrhea, confirmation with more than 1 FSH measurement is required.
- Females on HRT and whose menopausal status is in doubt must discontinue HRT to allow confirmation of postmenopausal status before study enrollment.

